Overview: Design and Methods. This three-year development project consists of 3 stages. **Stage one** (months 1-6) involves establishing a Development Team (DT) that will review the initial draft of TAPES and provide feedback to ensure that TAPES is acceptable to teachers and feasible for the school setting. **Stage two** (months 7-20) involves two successive open trials of the TAPES protocol with 15 teachers and 20 children. This stage will allow for "trial runs" of the training to assess feasibility, acceptability and utility of the training. Data and qualitative feedback gleaned during the first open trial will inform modifications for the second open trial. We will present and discuss data with the DT after each open trial. We will also ask 5 teachers from open trial 1 to test out the revisions for open trial 2. Based on knowledge gained in this stage, appropriate modifications will be made for stage three. **Stage three** (months 21-34) involves a pilot RCT using a randomized controlled design comparing TAPES to the Teacher Anxiety Training (TAT). TAT (developed by the PIs for use in other studies and described below) will be used to represent "typical" teacher professional development training. The RCT will be conducted in three phases. Phase 1 consists of recruiting, randomizing, and training

teachers in either TAPES or TAT. Also during this phase (but after the training), teachers will recruit anxious children and study staff will screen and evaluate them to determine eligibility. In Phase 2 teachers will implement TAPES or TAT. Phase 3 involves a post-intervention (after 8 weeks) and a three-month follow-up assessment of the primary (teacher behavior) and secondary (child) outcomes. Trained independent evaluators (IEs) will assess primary outcomes (teacher behavior). The culmination of these iterative stages will be a final version of the training that will be ready for evaluation in a larger efficacy trial.

DETAILED DESCRIPTION OF EACH STAGE

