
Phase 1 - Recruitment, Randomization, Training, Student Screening, and Baseline

Evaluations: In Phase 1, teachers will be randomly selected from the pool of interested participants and randomized to TAPES or TAT. Once randomized, teachers will complete their assigned training. Teachers will then identify potentially eligible students from their classes and provide information about the study to their parents. Interested parents will contact study staff and complete a brief phone screen. Students who appear eligible based on the phone screen (e.g.,

have elevated anxiety; are in elementary school) will be invited to complete informed consent and a full baseline evaluation with an IE (see Table 1 for measures). Families who "pass" the baseline evaluation (i.e., student obtains a *t* score of 60 on Spence Children's Anxiety Scale (SCAS) and/or a CSR of at least 3 on the ADIS-V) will be considered eligible (see Inclusion/Exclusion criteria below).

Phase 2 – TAPES/TAT Implementation: Teachers will implement TAPES or TAT depending on their random assignment over 8 weeks from child enrollment.

Phase 3 - Post- and Follow-up Evaluations: At the end of the 8 weeks, teachers and children in both groups will complete a post evaluation (see Table of Measures). Teachers, students, and parents will complete a TAPES satisfaction measure and provide feedback to enhance the protocol. Teachers will complete an exit interview. Students who need mental health services will be referred to the school counselor or community provider for treatment. A 3 month follow-up evaluation to assess sustained use of TAPES/TAT skills will be conducted.

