burnout, teacher efficacy; teacher behavior) and child characteristics (e.g., gender, age, baseline anxiety symptoms, classroom functioning). To test the main hypothesis, that teachers in TAPES, compared to TAT, will have higher knowledge about anxiety reduction, we will examine scores on the *Teacher Knowledge Assessment* at post-training, and at the end of school year as outcomes in GLM controlling for teacher pre-training score. Let y_i denote the post-training or end of school year test score of teacher i, x_{i1} and x_{i2} denote teacher i's group assignment and pre-training test score, respectively, and ε_i denote resident term. Rejecting $\beta_1 \leq 0$ and $\beta_3 \leq 0$ in the model: $y_i = \beta_0 + \beta_1 \times x_{i1} + \beta_2 \times x_{i2} + \beta_3 \times x_{i1} \times x_{i2} + \varepsilon_i$ suggests that TAPES teachers' post-training test scores are higher and they have a greater gain in knowledge than TAT teachers. Teacher-specific covariates can be added to the above model as needed. To test the hypothesis that TAPES, compared to TAT, will result in greater use of anxiety reduction skills in the classroom, IE's Classroom Observation of Teachers Skills rating for each pair of teacher and anxious student at baseline, post-intervention, and 3-month follow-up will be modeled in GLMM. Now rating, y_{ijk} are nested within teacher k and student j, who is nested within teacher k, in the multilevel equations: Level 1: $y_{ijk} = \pi_{0jk} + \pi_{1jk} \times \text{timepoint}_{ijk} + e_{ijk}$; Level 2: $\pi_{0jk} = \beta_{00k} + r_{0jk}$ and $\pi_{1jk} = \beta_{10k} + r_{1jk}$; Level 3: $\beta_{00k} = \gamma_{000} + \gamma_{001} \times w_k + u_{00k}$ and $\beta_{10k} = \gamma_{100} + \gamma_{101} \times w_k + u_{10k}$; where w_k denotes teacher k's intervention-training group assignment with e, r, and u representing error terms in the respective levels. Teacher-specific (e.g., years of teaching experience, teaching efficacy) and child-specific (e.g., age, baseline anxiety severity) covariates can be added to Levels 2 and 3 equations as needed. Aim #4 (Secondary Outcomes): To examine the impact of TAPES relative to TAT on student outcomes. Change scores on student mental health (e.g., Spence Children's Anxiety Scale, SCAS) and academic achievement (e.g., Woodcock-Johnson Tests of Achievement) from pre-to postintervention and 3-month follow-up will be modeled as GLMM similar to above in Aim 3. **Exploratory aims**: To examine mediators (proposed in the theory of change, see Figure 1 in Appendix) and predictors and moderators (e.g. Teacher Background Form, MBI-Educators Scale) of TAPES impact on teacher knowledge and behavior. Structural equation modeling (SEM) will be used to explore potential predictors (e.g., baseline teacher burnout as measured by MBI-ES), mediators (e.g., subscale scores from the OSTES) and moderators (e.g., years of teacher experience) on teacher behavior change (e.g., change score on the Classroom Observation of Teachers Skills at pre-, post-intervention and 3-month follow-up). Sub study: Aim #1: Assess the direct and indirect cost of pediatric anxiety among youth enrolled in the TAPES intervention. This aim involves the modification of existing measures of direct and indirect cost. These measures will be administered to parents and teachers at existing TAPES assessment time points (i.e. baseline, post intervention and three-month follow up). Aim #1a: Estimating the cost of pediatric anxiety through direct and indirect costs. Aim #2: To examine the child and parent benefit of TAPES compared to UC. This aim involves estimating the cost of TAPES relative to the UC condition in relation to direct and indirect costs. Exploratory Aim: To examine family demographic factors as moderators of pediatric anxiety cost. **Power Analysis.** Although this is a development study proposing a small pilot RCT, attempts were made to estimate statistical power for the key outcomes based on existing literatures on similar measures (see White et al., 2011 for Teacher Knowledge Assessment and Barrett et al., 2005 for child anxiety using the SCAS). Using Optimal Design version 3.0 calculations for both variables were based on an anticipated enrollment of 20 teachers in each group (and 1-2 students per teacher). We assumed a conservative within-teacher ICC of 0.10 (Eldridge et al., 2004) and

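### The classroom-skills primary model most likely starts from a post-training baseline and names neither the tested contrast nor the time coding; a group-by-time slope test would drop any training effect already present at BL

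*Combined protocol and SAP*

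**What the plan says.** **Skills model (Data Analytic Plan, Aim #3).** The observer's "rating for each pair of teacher and anxious student at baseline, post-intervention, and 3-month follow-up will be modeled in GLMM". Level 1 has one timepoint term with one slope. Level 3 lets training group act on the intercept (γ001) and on the slope (γ101). No null hypothesis is attached to either coefficient. Timepoint is not defined as visit number, weeks or categories. Teacher and child "covariates can be added to Levels 2 and 3 equations as needed".

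**Knowledge model (same section).** Test scores enter "as outcomes in GLM controlling for teacher pre-training score", and the coefficients to be tested, β1 and β3, are named.

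**Order of events.** Stage 3, Phase 1: "Once randomized, teachers will complete their assigned training. Teachers will then identify potentially eligible students from their classes". The Overview of Design and Methods agrees: "Also during this phase (but after the training), teachers will recruit anxious children and study staff will screen and evaluate them". Phase 2 implementation runs "depending on their random assignment over 8 weeks from child enrollment".

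**Table 1.** The classroom observation appears in three rows. The primary-outcome and fidelity rows list BL, PO and FU. The usability row lists Pre-Training as well as BL, PO and FU. According to the Measures section, the battery serves Stages 2 and 3 together. The Teacher Knowledge Assessment is listed at BL and PO only.

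**Other uses of the rating.** The equivalence check covers "burnout, teacher efficacy; teacher behavior) and child characteristics". The exploratory models use a "change score on the Classroom Observation of Teachers Skills at pre-, post-intervention and 3-month follow-up".

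**The concern.** A baseline in a randomized comparison should precede the randomized intervention. Here the arms differ in the training itself: one experiential day of about eight hours for TAPES against a three-hour didactic session for TAT. If the first modelled rating follows that training, part of the effect may already be in it.

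In a model with group, linear time and their product, the customary test is the product term. That term measures how far the arms move apart after BL, so any earlier separation goes into the intercept difference, where it cannot be told apart from chance imbalance between 40 teachers. The skills effect would then be understated. An equivalence check on teacher behavior made at BL would mix training effect with imbalance in the same way.

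Because no coefficient is named, an analyst could also choose between γ001 and γ101 after seeing the data.

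**Working it through.** **1. The plan's own figure.** None exists for skills. The nearest is knowledge: 80% power at d = 1.19 with 20 teachers per group. A two-sided 0.05 comparison of 20 v 20 at d = 1.19 gives 96% (normal) or 95.6% (t-test), so 80% holds only as a lower bound. This is a separate matter and is not used below.

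**2. When BL falls.** Three statements, side by side:
- Students are identified after training (Overview; Stage 3, Phase 1).
- The skills rating belongs to a teacher-student pair (Aim #3), and a pair cannot exist before its student is enrolled.
- For this instrument the usability row separates Pre-Training from BL.

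These point to a post-training BL. Against them, the knowledge test is listed at BL in Table 1 but analysed against a pre-training score, so BL appears to mean pre-training for that measure. The label is undefined and probably has two meanings.

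**3. What the slope keeps.** Let the between-arm difference be f·d at BL and d at both PO and FU. Then

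(f·d, d, d) = d·(1, 1, 1) − (1−f)·d·(1, 0, 0).

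A constant difference is absorbed by γ001 and adds nothing to γ101. The slope is therefore proportional to 1−f, whatever the time coding, correlation or random slopes: 90%, 75% and 50% of its value at f = 0.1, 0.25 and 0.5.

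**4. Time coding matters even at f = 0.** The least-squares slope through (0, d, d) is 0.5d per visit with time 0, 1, 2, which puts the fitted gain at PO at 0.50d. With weeks 0, 8, 21 (three months taken as 13 weeks) the slope is 0.0430d per week, and the fitted gain at PO is 8 × 0.0430d = 0.34d. The actual gain is d in both cases.

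**5. Power of the slope test (illustration only).** The documents give no effect size or SD for skills. Assume 20 teachers per arm, two-sided 0.05, correlation r = 0.5 between visits, unit SD, and d = 0.91, chosen to give 80% at PO. With slope weights w, the variance is (1−r)·Σw²·2/20.
- Time 0, 1, 2: Σw² = 0.5; SE = √(0.5 × 0.5 × 0.1) = 0.158; slope = 0.455(1−f).
- Weeks 0, 8, 21: Σw² = 1/224.67 = 0.00445; SE = √(0.5 × 0.00445 × 0.1) = 0.0149; slope = 0.0392(1−f).

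Noncentral t, 38 df:

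| Time coding | f = 0 | f = 0.1 | f = 0.25 | f = 0.5 |
|---|---|---|---|---|
| 0, 1, 2 | 80% | 71% | 56% | 29% |
| weeks | 73% | 63% | 48% | 25% |

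With r from 0.3 to 0.7, the f = 0.5 figures range over 22–44% (visits) and 19–38% (weeks).

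With the plan's nesting, take 10 teachers with one student and 10 with two per arm, variances of 0.4 (teacher), 0.1 (student) and 0.5 (residual), and random slopes from none to moderate. At f = 0, 0.25 and 0.5 power is 79–93, 55–73 and 29–40% with visits, and 72–88, 48–65 and 24–35% with weeks. These variances imply a within-teacher ICC of 0.4/1.0 = 0.4 at one time point, against the plan's 0.10.

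**6. A PO contrast not conditioned on BL.** f does not enter, because d at PO is held fixed.
- Teacher level: 0.91/√(2/20) = 2.88, power 80%.
- Nested, no random slopes: the variance is 1.0 for a teacher with one student and 0.4 + 0.6/2 = 0.7 for one with two. Information per arm is 10/1.0 + 10/0.7 = 24.3, SE = √(2/24.3) = 0.287, and 0.91/0.287 = 3.17, power 87%.
- Teacher level with a Pre-Training covariate correlated 0.1 to 0.5 with PO: variance 2(1−r²)/20, 37 df, power 80.4% to 89.9%.

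Naming the PO contrast removes the dependence on f. The covariate then adds about 0 to 10 points.

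**The case against.** Four stronger readings are tempting, and the documents do not support them.

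**That BL is certainly post-training.** No section defines BL for teacher measures, and the knowledge row points the other way. The form rates the teacher in ordinary lessons, so a rating made before training could in principle be carried into each pair as its baseline. Post-training remains the more natural reading, because the unit is the pair and the usability row lists both time points. It is still an inference.

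**That the plan discards the training effect.** The model contains γ001, which carries the arm difference at the time origin. The loss arises only if γ101 alone is the test, and the plan does not say so. This objection stands, and for that reason the missing contrast is half of the point.

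**That the loss is large.** Before BL the arms differ only in their training, and TAT teachers are trained too. Consultation, in-class coaching and conjoint meetings all follow student enrollment, and the theory of change stresses feedback and implementation. A small f is plausible, though not shown.

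**That a Pre-Training observation is needed to repair the analysis.** It is not. Teachers are randomized, so a PO difference not conditioned on BL needs no pre-training measure to avoid this bias. Nor does Table 1 establish that Pre-Training is taken in the RCT, since it covers the open trials as well.

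It is also fair to say that this is a small pilot whose battery may be modified. That lowers the stakes for power, but a pilot meant to lead to an efficacy trial still needs an effect estimate whose meaning is fixed in advance.

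**Conclusion.** The point holds in a conditional form. For the skills outcome BL is undefined and most likely post-training, Table 1's rows disagree, and neither the tested coefficient nor the time coding is stated. If γ101 is the test and the arms already differ at BL, the slope keeps 1−f of its value. That identity assumes equal arm differences at PO and FU; f itself is unknown. The power figures show scale under invented inputs and do not forecast this trial's power. The matter should be fixed because it concerns a stated primary outcome and the remedy is cheap. It does not invalidate the trial.

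**What to change.** 1. Define BL for the classroom observation, stating whether it comes before or after training, and reconcile the three Table 1 rows.
2. Code time as categorical and name the between-arm difference at PO as the primary skills test, without conditioning on a post-training BL or forcing the arms to be equal there. Keep the student-within-teacher nesting as random intercepts. With only PO and FU as outcomes, a student random slope cannot be separated from the residual. Keep a post-training BL as a descriptive measure, and leave the PO and FU clock as it is.
3. Where the Pre-Training observation is taken in the RCT, enter it as the teacher-level covariate for precision. Use it instead of BL for the teacher-behavior equivalence check and the exploratory change scores.

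**Cost.** Steps 1 and 2 are text changes and need no new data. Step 3 is also text if Pre-Training is already planned for the RCT. If it is not, adding it is optional: up to 40 observations of 30 minutes, or 20 observer hours.

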
Feasibility of TAPES Implementation in Schools. In light of the similarities between TAPES and school-home collaborative models (i.e., conjoint meetings) we used data from these studies as a measure of feasibility of TAPES. Sheridan and colleagues (2012) demonstrated the efficacy of conjoint behavioral consultation (CBC), a structured intervention in which parents, teachers, and other support staff meet conjointly and use a structured collaborative problem-solving method to address academic, social or behavioral difficulties evidenced in the classroom (Sheridan & Kratochwill, 2007). In their large RCT, students (N = 272, in 82 general education classrooms) were randomized to CBC in which 4-5 conjoint meetings (each lasting between 45-60 minutes) occurred over an 8 week period or usual care (UC; existing school services). Relative to UC, children in CBC showed greater increases in adaptive behaviors and social skills based on both parent and teacher reports. Teachers in CBC, compared to UC, reported greater positive changes in their relationships with parents. Results from this RCT supported earlier uncontrolled trials (Sheridan et al., 2006; 2001) which included children in grades K-9 who had academic and

behavioral difficulties. Effect sizes were robust across all studies and ranged from .4-1.00. Moreover, parent and teacher ratings of satisfaction and acceptability were high (Sheridan et al., 2001). Surveys of school psychologists, parents, and teachers also indicated a preference for a collaborative model over a teacher-only or parent-only intervention model (Freer & Watson, 1999; Sheridan & Steck, 1995). Pfiffner and colleagues (2007) developed the Child Life and Attention Skills program (CLAS) for youth with ADHD. Relevant here, CLAS included 4-5 parent-teacher-student conjoint meetings (each 30 minutes long) in addition to other components. In their RCT, measures of treatment acceptability by parents, students, and teachers were positive. Attendance in CLAS was high-- teachers completed an average of 4.7 conjoint meetings. In sum, these studies support the feasibility and acceptability (i.e., high attendance, high ratings of intervention satisfaction) of implementing a teacher–parent-student collaborative approach.

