Stage 1: Establish DT and refine initial version of the TAPES Protocol. The DT will strive to ensure that the teacher training will be acceptable, feasible, and usable in the school setting. DT Composition: The DT will consist of the PIs (Drs. [name] & [name]), two national experts in teacher training (Drs. [name] & [name]), two experts in school-home collaborative interventions (Drs. [name] & [name]), and two experts in training school-based personnel in CBT techniques for anxious youth (Drs. [name] and [name]). A representative from the CT Department of Education ([name]), a CT school psychologist ([name]), and two CT elementary teachers (TBN) will complete the DT. See Appendix for letters of support. DT Procedures and Analysis: DT members will be provided with all materials at least one month prior to the first meeting so they can review the initial protocol. Next, DT members will participate in a half day meeting during which the PIs will present an overview of all study components (e.g., rationale, training strategies, methods for teacher observations). The meeting will take place using an interactive web conferencing site that enables real-time Q&A. DT members will provide detailed feedback about the TAPES strategies, study methods/measures, perceived barriers to successful implementation and adoption by teachers, and solutions to potential barriers. Information from this meeting will be used to revise the protocol in preparation for the first open trial. Within four weeks, a revised version of the protocol will be distributed to the DT for another round of revisions during a second meeting. A similar procedure will be used for each successive revision of the protocol. Stage 2: Open **Trials.** During Stage 2, teachers and IEs will be trained and will conduct two sequential open trials. Study staff will engage in screening activities of students and IEs will complete baseline evaluations on referred students. The purpose of the open trials is to evaluate the feasibility of the training, modify methods as needed, allow teachers to implement the skills learned in the training and receive real time coaching and consultation with anxious children. Data on TAPES usability, acceptability, fidelity, satisfaction, and teacher and child outcomes will also be collected (see Measures below). After each open trial, feedback (via exit interviews and standardized measures) from teachers, students, and parents will be integrated by the research team and presented to the DT for another revision of the protocol. Teachers will be asked to participate in an exit interview after they implement TAPES with an anxious child. Stage 3: Pilot RCT. In stage 3, we will conduct a pilot RCT with 40 teachers and a maximum of 60 anxious youth. The RCT will be conducted in 3 phases.

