Sub study: From an economic perspective, anxiety confers a high economic burden on the individual, state and national level. Based on data from 2002, the annual cost of anxiety disorders in the United States is likely to be more than \$100 billion. These cost estimates are 16 years old and an updated examination of the cost of pediatric anxiety disorders is needed. Research has not investigated the potential financial benefit (e.g. school attendance, standardized test scores) or fiscal feasibility of adopting these interventions relative to current practices. Within the United States, it is also uncertain whether the cost burden of pediatric anxiety varies by demographic factors (e.g. minority status, socio-economic status, gender). Each of these cost factors represent sizable gaps in scientific knowledge. In this context, a Pre-K award was submitted to the Connecticut Institute for Clinical and Translational Science in order to fill this important gap in the scientific literature. This sub study will examine the cost of pediatric anxiety and the relative benefit of TAPES compared to usual care (UC). The purpose of this costs and benefits analysis is to provide information to school system administrators and teachers regarding the budgetary consequences of pediatric anxiety and to summarize the cost of achieving potential improvements in school functioning.

Procedures for Summer Months. We will only randomize teachers and enroll students if at least 10 weeks of school remain in the academic year to allow sufficient time to complete baseline evaluation, TAPES implementation and post evaluations.

Randomization. During the RCT, randomization will occur at the teacher level at a 1:1 (20 TAPES: 20 TAT). The randomization plan will be generated prior to the identification of teachers to minimize potential biases. Randomizing teachers to two active training conditions was selected for several reasons. The current design allows for all teachers to receive some training in anxiety identification and reduction—a major recruitment barrier in our previous school-based trials where clinicians or nurses were assigned to a no training control condition and subsequently dropped from the study. In addition, this design allows for an examination of a brief teacher training which represents typical teacher professional development offerings in CT.

Participants and Recruitment

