TAT: TAT is a 3-hour didactic training on student anxiety that the PIs use in their ongoing school-based studies for school clinicians and nurses (modified for teachers). The TAT content will include information on the signs, causes, consequences, and effective interventions for student anxiety. As noted earlier, this control condition was selected to enhance teacher recruitment and mimic the format of teacher professional development trainings in CT. Thus, TAT will provide a credible and acceptable control. An added value of this proposal will be to examine the impact of TAT on teacher behavior and child outcomes relative to TAPES. Independent Evaluator (IE) Training. IEs will have a masters or doctoral degree in a relevant child mental health field and experience with conducting diagnostic assessments with anxious youth. Training and certification of IEs will include completion of: 1) didactic training that includes review and practice of all assessment measures and study procedures by the PIs, 2) review of ADIS videotaped administrations by a senior interviewer, 3) achieving inter-rater reliability (kappa) of .85 for the severity ratings on 3 cases (live or with videotapes) and 4) administration of the ADIS in the presence of a senior interviewer. All assessments will be videotaped and a random 15% of tapes will be evaluated for interrater reliability (i.e., for the severity ratings).

Measures. The selection of proposed measures to be used in Stages 2 and 3 was guided by the best available measures for the study aims and proposed theory of change, and participant burden. Measures, informants, and time points are listed in Table 1. Data will be collected from multiple informants (e.g., teacher, IEs, parent, child) using multiple formats (e.g., classroom observations, rating scales, interviews, school records). *Many of the measures were used in the*

PI's previous school-based intervention development studies and will be modified for TAPES. The assessment battery will also be modified based on DT and open trial feedback. Measures to be developed and used in the sub-study are also included in this section.

Primary Outcomes: Teacher Knowledge and Skills

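### The cost sub-study names usual care as its comparator, but the trial can only compare TAPES with TAT, and no usual-care definition or data source is given

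*Combined protocol and SAP*

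**What the plan says.** The Sub study paragraph in the Research Plan says that the sub-study will look at the cost of pediatric anxiety and "the relative benefit of TAPES compared to usual care (UC"). The results are meant to inform school administrators and teachers about budgets and about what improvements in school functioning would cost. The Data Analytic Plan repeats the comparator in sub-study Aim #2: "To examine the child and parent benefit of TAPES compared to UC". It then adds: "This aim involves estimating the cost of TAPES relative to the UC condition in relation to direct and indirect costs".

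The trial itself is described differently. Under Stage 3, "we will conduct a pilot RCT with 40 teachers and a maximum of 60 anxious youth". The Randomization section allocates the teachers 1:1 to TAPES or TAT, describes both arms as active trainings, and explains why there is no untrained control: "The current design allows for all teachers to receive some training in anxiety identification and reduction". Under Intervention Conditions, "TAT is a 3-hour didactic training on student anxiety", covering signs, causes, consequences and effective interventions.

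**The concern.** The sub-study refers to a condition that the trial does not contain. The main comparative aims (Aims #1, #3 and #4) all compare TAPES with TAT, and only the sub-study says UC. The document's one definition of the term, "usual care (UC; existing school services"), belongs to a cited trial of another intervention, described under Feasibility of TAPES Implementation in Schools.

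The label matters because of who will read the result. An administrator who sees a cost or benefit stated against usual care will take it as a comparison with what the district does now. If the control group was in fact given a study-supplied anxiety course, the figure answers a different question: what TAPES adds over a short anxiety training, and at what extra cost.

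**Working it through.** **1. Count the arms.** The Stage 3 text gives 40 RCT teachers, and the Randomization section gives 20 TAPES and 20 TAT. 20 + 20 = 40, which reproduces the stated total. Teachers left for usual care: 40 − 20 − 20 = 0. Students enter through enrolled teachers, so there are no concurrent usual-care students either. The open trials in Stage 2 have no control group.

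**2. Look for another usual-care source.** The sub-study measures (the attendance, discipline and missed-work questionnaire, the Child Health Utility measure and the modified Service Utilization Form) are collected from study participants at study time points (Sub Study Measures, Table 1, Aim #1 of the sub-study). No historical, external or modelled usual-care data are described.

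**3. Write down what the data identify.** For cost C and effect E:

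- C(TAPES) − C(UC) = [C(TAPES) − C(TAT)] + [C(TAT) − C(UC)]
- E(TAPES) − E(UC) = [E(TAPES) − E(TAT)] + [E(TAT) − E(UC)]

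The trial estimates the first bracket on each line. Nothing in the plan estimates the second.

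**4. Size of the error if the first bracket is reported as the whole.** Let a = C(TAT) − C(UC) and b = E(TAT) − E(UC). The cost difference is then wrong by a and the benefit difference by b. A cost-to-benefit ratio would be reported as ΔC/ΔE when it should be (ΔC + a)/(ΔE + b).

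- a combines TAT's delivery cost, less any training cost already in usual care, with any change that TAT causes in services, absence and parents' missed work. Its sign is not fixed.
- b is positive if TAT helps students more than usual care does, and zero if it does not. The documents give no estimate.
- If a = 0 and b = 0 there is no error.

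**5. Test whether TAT can be taken as usual care from the text.**

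| Points towards TAT as usual care | Points away |
|---|---|
| The aims summary calls it a standard professional development condition. | The Randomization section calls both arms active and sets them against the untrained controls of the team's previous trials. |
| The design overview and the Randomization section say it represents typical professional development. | The TAT description says it mimics the format of such training, while its content is specific to anxiety. |
| The child eligibility text says that children of TAT teachers may get no evidence-based help. | In the preliminary survey, 0% of 13 respondents reported specific training in anxiety reduction techniques. |
| Students already in services are enrolled and service use is recorded. | Children found to need treatment are referred in both arms, which ordinary care would not prompt in the same way. |

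No sentence states that UC means TAT.

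**The case against.** The strongest reply is that UC is simply a loose label for TAT. Aim #2 speaks of a UC condition, TAT is the only condition other than TAPES, and the protocol several times presents TAT as ordinary professional development. At child level the TAT arm may also sit close to existing care. On this reading the contrast is estimable as planned and only the wording needs attention. The sub-study is also tied to a separate award application, which is not among the documents and may define UC.

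Much of this stands. The reading is plausible, and a reader who infers that the sub-study's comparison cannot be estimated at all goes too far, because TAPES versus TAT can be. But the protocol never makes the equation, and the right-hand column above counts against it. If TAT was meant, the text should say TAT, because usual care will be read as current practice.

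The survey should not be pressed too hard. It covers 13 teachers and school personnel and asks about specific training in anxiety reduction. It does not show that districts now provide nothing.

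**Conclusion.** The point holds as a mismatch between the sub-study's stated comparator and the trial's arms. As planned, the trial supports TAPES versus TAT. A result stated against usual care would be mislabelled unless TAT and usual care have the same costs and effects, which the documents do not show. The possible error cannot be sized or signed from the documents.

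A reader might infer two stronger conclusions that the documents do not support:

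- **That the benefit is understated by a definite factor.** If TAT gives a share s of TAPES' benefit over usual care, TAPES minus TAT is (1 − s) of that benefit, so the factor is 1/(1 − s). Assumed values of s = 0, 0.25 and 0.50 give 1.0, 1.33 and 2.0. No value of s comes from the documents, and zero is possible.
- **That the incremental cost is understated by the whole cost of TAT.** That would require usual care to contain no training cost and TAT to change no later service use, absence or missed work. Neither is stated.

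The issue is confined to the cost sub-study. Randomization, the primary teacher outcomes and the student outcomes are untouched.

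**What to change.** Restate the sub-study description, Aim #2, its analysis and its conclusions as TAPES versus TAT. Count the delivery cost of both trainings, including trainer and teacher time and, for TAPES, consultation and coaching. If a comparison with usual care is still wanted for administrators, present it only as a labelled model-based scenario, with usual care defined and its data source and assumptions stated.

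No new arm, participants or visits are needed. The price is a narrower claim and a small amount of work to log training delivery time. That log should be planned, since no existing record is described that would supply it: the Teacher Time Log covers time spent with study students, not the delivery of the trainings.
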